6.4.12 Early Termination

Early termination of a subject from the study may occur due to loss to follow-up or withdrawal of consent by the subject. In accordance with legal requirements and International Conference on Harmonization (ICH) – Good Clinical Practice (GCP) guidelines, every subject or his/her legal representative has the right to withdraw from the study at any time and without providing reasons. If provided, the reason (adverse event, study burden, lack of efficacy, other) a subject withdrew consent will be recorded in the electronic Case Report Form (eCRF). Attempts to contact subjects who are suspected of being lost to follow-up must be documented in the subject's source documents.

7 ASSESSMENT OF SAFETY

7.1 Definitions

7.1.1 Adverse Event

An AE is any untoward medical occurrence associated with the use of a drug in humans, whether or not considered drug related. An AE can be any unfavorable and unintended sign (e.g. an abnormal laboratory finding), symptom, or disease temporally associated with the use of a drug, without any judgment about causality.

AEs include treatment emergent exacerbations of pre-existing illnesses and AEs that occur as a result of protocol-mandated interventions.

7.1.2 Serious Adverse Event

An AE is considered "serious" if it results in any of the following outcomes:

• Death

- Life-threatening AE (i.e. the subject was at immediate risk of death from the event as it occurred. An event that might have led to death if it had occurred with greater severity is not "life-threatening")
- Inpatient hospitalization or prolongation of existing hospitalization
- Persistent or significant incapacity or substantial disruption of the ability to conduct normal life functions
- Congenital anomaly/ birth defect
- Important medical event (i.e. an event that may not result in death, be life-threatening, or require hospitalization, but which may be considered serious by the investigator or Sponsor, as it may jeopardize the subject and may require medical/surgical intervention to prevent one of the outcomes listed above). Examples of such medical events include allergic bronchospasm requiring intensive treatment in an emergency room or at home, blood dyscrasias or convulsions that do not result in inpatient hospitalization, or the development of drug dependency or drug abuse.

The following are not considered SAEs: a visit to the emergency room or other hospital department < 24 hours that does not result in admission (unless considered an important medical or life-threatening event), an elective surgery planned prior to signing consent, admission as per protocol for planned medical/surgical procedure, and/or routine health assessments requiring admission for baseline/trending of health status (e.g. routine colonoscopy).

The terms "severe" and "serious" are not synonymous. Severity refers to the intensity of an AE (e.g. mild, moderate, or severe pain); the event itself may be of minor medical significance (e.g. severe back pain). "Serious" is a regulatory definition, as defined above. Seriousness (not severity) serves as the basis for defining regulatory reporting obligations.

Severity and seriousness should be independently assessed when recording AEs and SAEs on the eCRF.

7.1.3 Abnormal Physical Exam, Laboratory, Vital Sign, and Electrocardiogram Findings

Abnormal physical exam findings that are clinically significant and are identified prior to the first dose of study drug should be recorded as medical history. New or worsening clinically significant abnormal physical exam findings identified after the first dose of study drug should be recorded as AEs.

Only abnormal laboratory, vital sign, and ECG findings that are considered clinically significant by the investigator (e.g. require active management or are associated with accompanying symptoms/signs) will be recorded as medical history or AEs on the eCRF. Abnormal laboratory, vital sign, and ECG findings that occur prior to the first dose of study

drug should be recorded as medical history, and abnormal findings that occur after the first dose of study drug should be recorded as AEs.

If the clinically significant laboratory, vital sign, or ECG abnormality is a sign associated with a confirmed disease or condition (e.g. elevated creatinine in a subject diagnosed with chronic kidney disease), only the diagnosis (chronic kidney disease) needs to be recorded on the AE eCRF (rather than listing individual test findings as AEs).

Separate instances of the same clinically significant laboratory, vital sign, or ECG abnormality across visits should not be recorded as separate AEs or SAEs.

7.1.4 Deaths

Any deaths that occur from the time of informed consent to the follow-up visit, regardless of attribution, must be reported within 24 hours of investigator's awareness of the death. See Safety Form Completion Instructions for complete instructions.

The Sponsor should be provided a copy of any post-mortem findings and/or relevant medical reports, including histopathology.

7.1.5 Pregnancies and Contraception Requirements for Females

For the purposes of this study, a female of childbearing potential is defined as any female who has experienced menarche and is pre-menopausal, unless permanently surgically sterile (e.g., hysterectomy, bilateral salpingectomy, bilateral oophorectomy). A postmenopausal state is defined as no menses for 12 months without an alternative medical cause in a previously menstruating female.

For the purposes of this study, acceptable contraception is defined below based on *Nonclinical Safety Studies for the Conduct of Human Clinical Trials and Marketing Authorization for Pharmaceuticals: ICH M3(R2)* dated January 2010, and other available guidelines ("U.S. Medical Eligibility Criteria for Contraceptive Use" 2010; "Recommendations related to contraception and pregnancy testing in clinical trials" 2014; "M3(R2) Nonclinical Safety Studies for the Conduct of Human Clinical Trials and Marketing Authorization for Pharmaceuticals" 2010):

All female subjects of childbearing potential must use highly effective contraception, which includes the use of one or more of the following acceptable methods:

- 1. Surgical sterilization (e.g., bilateral tubal occlusion or ligation, hysterectomy, bilateral salpingectomy, bilateral oophorectomy)
- 2. Total (as opposed to periodic or cyclic) abstinence from heterosexual intercourse, only if planned for the entire duration of the study period and consistent with the preferred and usual lifestyle for the subject
- 3. Hormonal contraception associated with consistent inhibition of ovulation; these may include (but are not necessarily limited to) oral, intravaginal, implantable, injectable, or transdermal delivery methods

- 4. Intrauterine device/system
- 5. Exclusive (sole) monogamous intercourse with a sterilized (i.e., vasectomized) or otherwise non-fertile (e.g., castrated) male partner; the male partner must have received medical assessment of the surgical success

Progesterone-only oral contraceptives are excluded as a highly effective method of contraception, as they do not consistently inhibit ovulation. Male or female condoms with or without spermicide, and female caps, diaphragms, and sponges with spermicide, or combinations (double barrier) are also excluded as highly effective contraceptive methods.

Any pregnancy occurring in a female subject or the female partner of a male subject, from the first study drug administration through the required follow-up visit must be reported within 24 hours of the investigator's awareness of the pregnancy. See Safety Form Completion Instructions for complete instructions.

The investigator will follow the pregnancy to delivery or other pregnancy outcome.

Pregnancy in a female clinical trial subject or female partner of a male clinical trial subject is not an SAE per se. Complications of such pregnancies (for example, spontaneous abortion) may qualify as SAEs and should be reported as such even if they occur after the follow-up visit. Any congenital anomalies/birth defects must be recorded and reported as SAEs. See Safety Form Completion Instructions for complete instructions.

7.1.6 Worsening of Pruritus or Underlying Pruritic Skin Disease

Pruritus or the underlying pruritic skin disease (PN, AD, or psoriasis) should be recorded as an AE or SAE only if considered by the investigator to have worsened in severity beyond the subject's typical fluctuations. It is important to include a description of the nature of the unexpected worsening when recording the AE or SAE (e.g. new PN lesions in previously uninvolved skin).

7.2 Methods and Timing for Recording and Reporting Adverse Events

7.2.1 Adverse Event Reporting Period

Any AE occurrence during the study must be recorded on source documentation and eCRF at the site, in accordance with protocol instructions.

AEs and SAEs will be recorded from the first study drug administration through the followup visit. After the 5-week follow-up visit, only SAEs that are believed to be drug-related should be reported.

After informed consent, but prior to initiation of study drug, only SAEs considered by the investigator to be caused by a protocol-mandated intervention will be collected (e.g. SAEs related to invasive procedures such as blood collection). These procedure-related SAEs should only be reported on the source documents and SAE form, not on the AE eCRF.

Subjects who undergo Baseline visit procedures but are not enrolled into the study will not have SAEs recorded in the clinical database.

7.2.2 Eliciting Adverse Events

Investigators will seek information on AEs and SAEs at each subject contact through the follow-up visit. All AEs and SAEs, whether reported by the subject or noted by authorized study personnel, will be recorded in the subject's medical record and on the AE eCRF page, and, if serious, on the SAE form. For each AE and SAE recorded, the investigator will make an assessment of seriousness, severity, and causality.

7.2.3 Assessment of Severity

All AEs entered into the eCRF will be graded for severity using the National Cancer Institute Common Terminology Criteria for Adverse Events (NCI CTCAE) v4.03 ("Common Terminology Criteria for Adverse Events (CTCAE)" 2010) to describe the maximum intensity of the adverse event.

If the AE cannot be found in the event-specific NCI CTCAE grading criteria, the investigator should use the definitions for Grade 1, 2, 3, and 4 in Table 1.

Grade	Severity	Alternate Description ^a
1	Mild (apply event-specific NCI CTCAE grading criteria)	Asymptomatic or mild symptoms; clinical or diagnostic observations only; intervention not indicated.
2	Moderate (apply event-specific NCI CTCAE grading criteria)	Minimal, local or noninvasive intervention indicated; limiting age-appropriate instrumental activities of daily living (ADL ^b)
3	Severe (apply event-specific NCI CTCAE grading criteria)	Severe or medically significant but not immediately life-threatening; hospitalization or prolongation of hospitalization indicated; disabling; limiting self care ADL ^c
4	Very severe, life threatening, or disabling (apply event-specific NCI CTCAE grading criteria)	Life-threatening consequences; urgent intervention indicated.
5	Death related to AE	

Table 1Adverse Event Grading

^a Use these alternative definitions for Grade 1, 2, 3, and 4 events when the observed or reported AE is not in the NCI CTCAE listing. A semi-colon indicates 'or' within the alternate description of the grade.

^b Instrumental ADL refer to preparing meals, shopping for groceries or clothes, using the telephone, managing money, etc.

^c Self care ADL refer to bathing, dressing and undressing, feeding self, using the toilet, taking medications, and not bedridden.

Source: National Cancer Institute Common Terminology Criteria for Adverse Events (NCI CTCAE) v4.03

Note that severity, a measure of intensity, is not equivalent to seriousness, a regulatory definition of outcome. Regardless of severity, some AEs may meet the criteria for seriousness. See Section 7.1.2 for the definition of an SAE.

If an adverse event changes in severity during the same study period (e.g., treatment period), only the highest severity grade will be recorded on the eCRF.

7.2.4 Assessment of Causality

The investigator's assessment of causality must be provided for all AEs (serious and nonserious). An investigator's causality assessment is the determination of whether there exists a reasonable possibility that the investigational product caused or contributed to an AE. Causality of an AE will be assessed by the investigator using the following terms:

- Likely Related: A reaction that follows a reasonable temporal sequence from administration of the study drug; that follows a known or expected response pattern to the suspected study drug; and for which other potential etiologies are considered less likely factors than the study drug.
- Likely Unrelated: A reaction that, considering all potential etiologies, is most likely due to factors other than the study drug.

7.3 Follow-up of Adverse Events and Serious Adverse Events

The investigator must make every effort to follow all AEs and SAEs regardless of attribution until judged resolved or stabilized, the subject is lost to follow-up, or it has been determined that treatment with study drug or participation in the study is not the cause of the AE or SAE.

7.4 Reporting Serious Adverse Events to the Sponsor and Institutional Review Board (IRB) or Ethics Committee (EC)

The Sponsor or designee is under obligation to report certain SAEs to regulatory authorities related to investigational drugs in clinical trials. The Sponsor or designee must be notified within 24 hours of an AE when the investigator determines that an AE meets the protocol definition of an SAE, regardless of the cause or relationship to study drug.

An SAE related to study participation occurring before study drug administration and after informed consent should be promptly reported to the Sponsor. If the investigator learns of any SAE at any time after a participant has been discharged from the study, and the SAE is considered likely related to study drug, the SAE should be promptly reported to the Sponsor.

Please see the Safety Form Report Completion Instructions for safety reporting instructions.

The investigator must also comply with applicable requirements concerning reporting of SAEs to the IRB or EC. This may include initial or follow-up notification of an SAE or other safety information.

7.5 Reporting Serious Adverse Events to Regulatory Authorities and Study Investigators

The Sponsor, or its designee, is responsible for submitting reports of serious, unexpected related adverse events to regulatory authorities on an expedited basis, according to the ICH E2A Guideline and to other regulatory authorities according to national and local regulations as required. The Sponsor, or its designee, is responsible for prompt submission to the IRB or EC of any expedited SAE reports submitted to regulatory authorities. All investigators participating in ongoing clinical studies with serlopitant will receive copies of the SAE reports submitted on an expedited basis to regulatory authorities.

8 STATISTICAL METHODS

All statistical processing will be performed using SAS® unless otherwise stated. No interim analyses are planned. Data will be summarized with descriptive statistics by visit. For continuous variables, the following information will be presented: n, mean, standard deviation, median, minimum and maximum. For categorical variables, counts and percentages will be used.

Baseline will be the last recorded value prior to the start of treatment.

A SAP describing all statistical analyses will be written as a separate document.

8.1 Handling of Missing Data and Excluded Therapy Use

Summary statistics will generally be reported based upon observed data. Should a determination of treatment period (on treatment, pre-treatment) be required for adverse events or concomitant medication but the corresponding date is missing, or is a partial date, the event/medication will be considered on treatment unless the portions of the date that are available indicate this is not possible.

8.2 Analysis Population

All subjects who receive at least 1 confirmed dose of study drug and have at least 1 postbaseline safety assessment will be included in the safety population. All analyses will be performed using the safety population.

8.3 Subject Disposition

An accounting of all subjects by disposition will be presented. Subjects who discontinue study drug prematurely or withdraw from the study will be summarized and listed, with a description of the reason for early termination/withdrawal.

8.4 Subject Characteristics

Demographic and other baseline characteristics will be summarized.

8.5 Concomitant Medications

Concomitant medications will be coded by the World Health Organization Drug Dictionary to Anatomical Therapeutic Classification (ATC) and preferred drug name. Concomitant medications will be summarized by ATC level and preferred drug name and listed.

8.6 Treatment Compliance and Extent of Exposure

Compliance with study drug dosing will be determined based on tablet counts recorded on the eCRF. Compliance will be calculated by analyzing expected number of tablets returned versus actual number of tablets returned. Summaries of treatment exposure will also be produced.

8.7 Efficacy Analyses

Descriptive statistics will be used to summarize the following:

- Change from baseline in WI-NRS to Weeks 4, 8, 20, 28, 36, 44, and 52
- Change from baseline in DLQI (symptoms and feelings, daily activities, leisure, work or school performance, personal relationships, and treatment) to Weeks 20, 36 and 52
- Change from baseline in IGA PN-S to Weeks 4, 8, 20, 28, 36, 44, and 52.

Data will be summarized by time point using frequency tabulations or descriptive statistics as appropriate. Observed results, as well as change from baseline will be summarized, as appropriate.

8.8 Safety Analyses

8.8.1 Adverse Events

All AEs will be classified by system organ class and preferred term using the Medical Dictionary for Regulatory Activities (MedDRA). TEAEs will be tabulated in a manner which provides information about the incidence of TEAEs for the entire treatment period as well as by time period in order to understand the evolution of TEAEs over time. Thus, in addition to the TEAE analysis over the entire 12-month treatment time, results will be presented for the following periods: 0 to 4 weeks, > 4 to 12 weeks, > 12 to 28 weeks, > 28 weeks to 36 weeks, > 36 to end of treatment, and end of treatment to end of the study (including by weekly periods from end of treatment to end of study). For incidence reporting, if a subject reported more than one TEAE that was coded to the same system organ class or preferred term, the subject will be counted only once for that specific system organ class or preferred term. An overview of AEs, which includes subject incidence of AEs, TEAEs, treatment-related TEAEs, TEAEs by severity, SAEs, deaths, and AEs leading to discontinuation, will be presented.

All information pertaining to AEs noted during the study will be listed by subject and will include a verbatim description of the event as reported by the investigator, as well as the preferred term, system organ class, start date, end date (if ended), seriousness, severity, action taken regarding the study drug, outcome, and relationship to the study drug. In addition, a listing of subjects who prematurely discontinue from the study due to AEs will be provided.

SAEs will be listed and summarized in a similar manner to AEs.

8.8.2 Clinical Safety Laboratory Results

Clinical safety laboratory values will be measured by a central laboratory. Summary statistics for actual values and for changes from baseline will be tabulated for laboratory results by scheduled visit. Graphs of laboratory values over time will also be produced, and listings will be provided.

Subjects with clinical laboratory values outside of the normal reference range at any postbaseline assessment will be summarized. Shifts from baseline laboratory values will be tabulated. A listing of all out-of-range laboratory test results, including assessment of clinical significance, will also be provided.

8.8.3 Vital Signs

The observed vital sign data and change from baseline for each scheduled visit will be summarized with descriptive statistics, and presented in a listing.

8.8.4 Electrocardiograms

The overall ECG assessment (abnormal or normal) will be summarized and descriptively characterized, along with a summary of how many subjects developed a post treatment abnormal result.

8.8.5 *Physical Exams*

Physical exam findings will be recorded by the sites within medical history or adverse events and otherwise not summarized, with the exception of weight and change from baseline in weight.

8.8.6 Menstrual Diaries

Menstrual diary dates will be used to summarize number and duration of menses.

8.8.7 Hospital Anxiety and Depression Scale

The observed data and change from baseline for the HADS will be summarized with descriptive statistics by scheduled visit. Both the Depression and the Anxiety subscales will be reported.

8.8.8 *Epworth Sleepiness Scale*

The observed data and change from baseline for the ESS will be summarized with descriptive statistics by scheduled visit.

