6.2.7 Assessment of Potential for Physical Dependence

NK₁-R antagonist dependence has not previously been described and therefore a drug classspecific, reliable and sensitive instrument for the assessment of withdrawal symptoms has not been developed. A surrogate assessment tool, such as those developed for opioid or benzodiazepine dependence, is not available.

In order to provide a comprehensive set of assessments for physical dependence and withdrawal symptoms following chronic exposure to the study drug, the HADS and ESS instruments will be administered at baseline and throughout the study period, as well as 3-days and 7-days following the last dose of study drug, and then weekly throughout the 5-week post-study drug observation period. In addition, vital signs will be assessed at each post-study drug observation visit, and an ECG and laboratory analyses will be assessed at the 5-week post-study drug visit. All TEAEs reported during this period will be medically reviewed to assess for possible physical dependence or withdrawal signs or symptoms.

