6.4.9 Week 52 Visit

The Week 52 Visit occurs 364 days (\pm 7 days) after the Baseline Visit. At the Week 52 Visit, the following procedures and assessments are to be performed:

- Register visit into the IWRS
- Review menstrual diary and record dates of menstrual flow (if applicable)
- Assess and record any AEs and/or SAEs
- Assess and record any changes in the subject's concomitant medications
- Female subjects should be queried for presence of new breast masses or abnormal discharge, and abnormal vaginal bleeding or discharge
- Perform targeted physical examination, including weight
- Obtain ECG
- Obtain vital signs
- Draw blood for clinical laboratory tests
 - Hematology

- Chemistry
- Endocrine
- Reproductive endocrine labs for females under 55 years of age at consent
- Perform a urine pregnancy test for females of childbearing potential (with positive or equivocal results to be confirmed by a serum pregnancy test)
- Ask subject to complete WI-NRS
- Ask the subject to complete the following questionnaires:
 - DLQI
 - HADS
 - ESS
- Perform IGA PN-S (for subjects with PN only)
- Obtain photos (only PN subjects that signed photography consent, only at sites selected for photography)
- Collect returned study drug
- Confirm next scheduled visit date

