# 5.2 Safety Endpoints

Safety endpoints include the following:

- Incidence of treatment-emergent adverse events (TEAEs) and serious adverse events (SAEs)
- Changes from baseline in clinical laboratory parameters
- Changes from baseline in vital sign and electrocardiogram (ECG) parameters
- Change from baseline in the Hospital Anxiety and Depression Scale (HADS)
- Change from baseline in the Epworth Sleepiness Scale (ESS)
- Assessment of physical dependence following chronic study drug exposure, in the monitored 5-week post-drug discontinuation period

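### Neither document defines a post-stop contrast for HADS and ESS: the protocol's only change score runs from the pre-treatment baseline, and the SAP leaves listings only

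*Protocol*

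**What the plan says.** Protocol Section 2 names physical dependence as a secondary objective. Protocol 3.3.1 and SAP 5.2 carry it as a safety endpoint, in the SAP's words: "Assessment of physical dependence following chronic study drug exposure, in the monitored 5-week post-drug discontinuation period".

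Protocol 6.2.7 sets out how it is assessed. HADS and ESS are given at baseline and during the study, "as well as 3-days and 7-days following the last dose of study drug, and then weekly throughout the 5-week post-study drug observation period". Vital signs are taken at each post-drug visit, with ECG and laboratory tests at five weeks, and "All TEAEs reported during this period will be medically reviewed to assess for possible physical dependence or withdrawal signs or symptoms".

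The analysis of the two scales is in Protocol 8.8.7, "The observed data and change from baseline for the HADS will be summarized with descriptive statistics by scheduled visit" (both HADS subscales), and 8.8.8, "The observed data and change from baseline for the ESS will be summarized with descriptive statistics by scheduled visit". Protocol Section 8 fixes the reference: "Baseline will be the last recorded value prior to the start of treatment".

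An on-drug value at the end of treatment exists for completers. At the Week 52 visit (6.4.9) the instruction "Ask the subject to complete the following questionnaires" covers DLQI, HADS and ESS. Appendix A schedules HADS and ESS at Baseline, Weeks 20, 36 and 52, the early treatment discontinuation (ETD) visit and all six post-drug visits.

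SAP v4 (12 May 2020) was shortened after early termination. Its Section 6.1.2 rules out any change-from-baseline summary, and 6.8.4.5 and 6.8.4.6 reduce HADS and ESS to by-subject listings. The HADS shell (Listing 16.2.7.2.1) has a row for each subscale. The ESS shell (Listing 16.2.7.2.2) shows the eight situations and no total.

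**The concern.** Withdrawal is worsening after stopping, relative to how the subject was on the drug. The natural reference for a post-drug score is therefore the last on-drug score. Against the pre-treatment value, the post-drug change also carries a year of other movement: itch relief, the standard therapy that Protocol 3.1 allows, and ordinary drift. A subject who improved on drug and then worsened on stopping can look unchanged, and one who drifted upward during the year can look as if stopping did harm.

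For roll-over subjects the reference is less certain still. Protocol 6.4.1 lets Baseline coincide with the final visit of a parent study. Whether that visit was drug-free is not settled: exclusion criterion 4 asks for a washout from investigational therapy, but the visit descriptions do not say how it applies to these subjects.

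SAP v4 removes the change score and puts nothing in its place. The endpoint stays in SAP 5.2 with no derived contrast behind it for these two scales.

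**Working it through.** The plan states no sample size calculation, threshold or effect size for HADS or ESS, so there is no figure to reproduce. The check is an identity, two worked cases and an illustration.

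**Identity.** Let B be the baseline score, E the Week 52 score and P a post-drug score. Then P − B = (E − B) + (P − E). Only the second term concerns stopping.

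**Two invented subjects.**
- B, E, P = 10, 5, 10: P − B = (5 − 10) + (10 − 5) = 0, while P − E = +5. Worsening on stopping is hidden.
- B, E, P = 5, 9, 9: P − B = (9 − 5) + (9 − 9) = +4, while P − E = 0. A rise appears with no change on stopping.

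**Illustration.** Scores were simulated on a 0–24 scale (the ESS total, 8 items × 3), rounded and cut off at the limits. All of these values are assumptions: baseline mean 8, SD 4, and equal correlations between the three scores of 0.5, 0.7 or 0.8. Ranges are across the correlations.

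| Shift on drug / after stopping | Mean P − B | Mean P − E | Rise ≥3 from B | Rise ≥3 from E |
|---|---|---|---|---|
| −3 / +3 | 0.0 | 2.8 | 16–26% | 53–55% |
| +3 / 0 | 3.0 | 0.0 | 55–57% | 16–27% |
| 0 / +3 | 3.0 | 3.0 | 55–57% | 55–57% |

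In the first row, 39–43% of those who rise by at least 3 from E show no rise from B. In the second, 22–25% of all subjects rise by at least 3 from B with no rise from E. In the third, with no on-drug shift, the two references agree. (The 2.8 falls short of 3 because scores are cut at 0.)

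**What visit means recover.** Mean P minus mean E equals the mean of P − E when the same subjects attend both visits, so the group shift can be read from observed means. The SD of the within-subject change and the share who worsen cannot. If attendance differs between visits, the difference in means also reflects who dropped out.

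**Two limits on any end-of-treatment reference.**
- On-drug scores are scheduled only at Weeks 20, 36 and 52. For a subject who stops just before Week 36 or Week 52, the last one is about 16 weeks old (36 − 20, or 52 − 36). A subject who stops before Week 20 has only the Baseline score. The ETD visit can fall up to 35 days after the last dose (6.4.10), so its score may be off drug.
- HADS asks about the prior week (6.2.5). At post-drug Day 3, about 7 − 3 = 4 of the recall days precede stopping.

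**The case against.** Four points on the other side have weight.

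First, the protocol sentences plan observed values as well as change, so Week 52 and post-drug means would both be tabulated. This stands at group level. It does not supply paired change, and withdrawal confined to a minority can disappear in a mean.

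Second, a reader might infer that HADS and ESS are the main tools for dependence and that the objective cannot be answered without this contrast. The documents do not support that. Protocol 6.2.7 describes a wider set with vital signs, ECG, laboratory tests and medical review of adverse events, and Protocol 8.8.1 adds weekly TEAE periods after treatment. SAP 6.8.2 keeps only whole-study incidence, but the TEAE listing still shows start days.

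Third, a reader might infer that the final report will print a misleading change from baseline. Under SAP v4 it will not. The listings also let a reader compare Week 52 with later visits subject by subject, directly for HADS and after summing eight items for ESS. What is missing is the derived contrast; the underlying scores are there.

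Fourth, a reader might infer that itch returning after stopping goes unmeasured, because Protocol 7.1.6 makes it an adverse event "only if considered by the investigator to have worsened in severity beyond the subject's typical fluctuations". Worsening beyond that limit is still recordable, and WI-NRS is taken at all six post-drug visits and shown in Listing 16.2.6.1. Only a change score is absent.

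A gain in precision should carry no weight here. With SD of change = SD × √(2(1 − r)), and assumed correlations of 0.5–0.6 a year apart and 0.75–0.8 weeks apart, the reduction runs from 21% (0.894 to 0.707) to 37% (1.000 to 0.632). The documents give no correlations, and no inferential analysis is planned.

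**Conclusion.** The point holds in a limited form. The protocol's only change score for the post-drug HADS and ESS visits uses a reference that mixes on-drug change with the effect of stopping. SAP v4 removes that score without a replacement while keeping the endpoint, so neither document gives a post-stop contrast for these scales. That the contrast can mask or mimic worsening follows from the identity alone. How often it would do so depends on how far scores move on drug, which the documents do not say: with no on-drug shift the references agree in the mean, and with an assumed 3-point shift the share rising by at least 3 points differs by about 27 to 41 percentage points (53 − 26 to 57 − 16). The data needed are already collected, at least for subjects who reach Week 52. This is a cheap improvement to the analysis. It does not show that the dependence objective fails.

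**What to change.** In Protocol 8.8.7 and 8.8.8 and SAP 6.8.4.5 and 6.8.4.6:

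- For subjects with a Week 52 score, add within-subject change from Week 52 to each post-drug visit for HADS anxiety, HADS depression and the ESS total, plus each subject's largest post-drug rise. One descriptive table is enough, or an added column in Listings 16.2.7.2.1 and 16.2.7.2.2. Show the ESS total in the latter.
- For early discontinuers, take as reference the last HADS and ESS completed on or before the last dose, print its date, and report these subjects separately. Do not use an off-drug ETD score as the reference. The printed date will also show where the only earlier score is the Baseline one, so that no on-drug reference exists.
- Footnote that the recall week of the Day 3 HADS overlaps days on drug.
- Optionally, show post-drug WI-NRS change from Week 52 in Listing 16.2.6.1.

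The cost is wording and a little programming, with no new data. The drawback is that the reference for early discontinuers is older and less comparable. Because the study was terminated early that group may be large, but the documents give no count.
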